APPENDIX B. INSTRUCTION TO PARTICIPANTS FOR HANDLING STUDY DRUG (ITACITINIB OR PLACEBO)

The participant must be instructed in the handling of study drug as follows:

- Store the study drug at room temperature.
- Only remove the number of tablets needed at the time of administration.
- Not to remove doses in advance of the next scheduled administration.
- Make every effort to take doses on schedule.
- Report any missed doses/lost tablets/capsules.
- Take study drug with a full glass of water.
- If the participant vomits after taking study drug, the participant should not take another dose.
- Keep study drug in a safe place and out of reach of children.
- Bring all used and unused study drug bottles/kits to the site at each visit.
- If a dose of itacitinib/placebo is missed by more than 8 hours, that dose should be skipped, and the next scheduled dose should be administered at the usual time.

APPENDIX C. DIAGNOSIS AND STAGING OF CHRONIC GVHD (NIH CRITERIA)

Signs and Symptoms of Chronic GVHD (Jagasia et al 2015)

Organ or Site	Diagnostic Feature(s) (Sufficient to Establish the Diagnosis of cGVHD)	Distinctive Features ^a (Seen in cGVHD, but Insufficient Alone to Establish a Diagnosis)	Other Features or Unclassified Entities (cGVHD Manifestations if Diagnosis is Confirmed)	Common (Seen With Both Acute and Chronic GVHD)
Skin	 Poikiloderma Lichen planus-like features Sclerotic features Morphea-like features Lichen sclerosus-like features 	DepigmentationPapulosquamous lesions	Sweat impairmentIchthyosisKeratosis pilarHypopigmentationHyperpigmenttaion	ErythemaMaculopapular rashPruritus
Nails		 Dystrophy Longitudinal ridging, splitting or brittle features Onycholysis Pterigium unguis Nail loss 		
Scalp and body hair		New onset of scarring or non-scarring scalp alopecia (after recovery from chemoradiotherapy) Loss of body hair Scaling	Thinning scalp hair, typically patchy, coarse or dull (not explained by endocrine or other causes) Premature gray hair	
Mouth	Lichen planus-like changes	 Xerostomia Mucoceles Mucosal atrophy Ulcers Pseudomembranes		 Gingivitis Mucositis Erythema Pain
Eyes		New onset dry, gritty, or painful eyes Cicatricial conjunctivitis Keratoconjunctivitis sicca Confluent areas of punctate keratopathy	 Photophobia Periorbital hyperpigmentation Blepharitis 	

Signs and Symptoms of Chronic GVHD (Continued)

Organ or Site	Diagnostic Feature(s) (Sufficient to Establish the Diagnosis of cGVHD)	Distinctive Features ^a (Seen in cGVHD, but Insufficient Alone to Establish a Diagnosis)	Other Features or Unclassified Entities (cGVHD Manifestations if Diagnosis is Confirmed)	Common (Seen With Both Acute and Chronic GVHD)
GI tract	Esophageal web Strictures or stenosis in the upper to mid third of the esophagus		Exocrine pancreatic insufficiency	 Anorexia Nausea Vomiting Diarrhea Weight loss Failure to thrive (infants and children)
Liver				• Total bilirubin, Alkaline phosphatase, ALT > 2 × ULN
Lung	Bronchiolitis obliterans diagnosed with lung biopsy Bronchiolitis obliterans syndrome (BOS) ^b	Air trapping and bronchiectasis on chest CT	Cryptogenetic organizing pneumonia (COP) Restrictive lung disease	
Muscle, fascia, joints	Fasciitis Joint stiffness or contractures secondary to fasciitis or sclerosis	Myositis or polymyositis (Diagnosis of cGVHD requires biopsy)	Edema Muscle cramps Arthralgia or arthritis	
Genitalia	Lichen planus-like features Lichen sclerosus-like features	 Erosions Fissures Ulcers		
Genitalia Females	Vaginal scarring or clotorial/labial agglutination			
Genitalia Males	Phimosis or urethral/meatus scarring or stenosis			
Hematopoietic and immune			 Thrombocytopenia Eosinophilia Lymphopenia Hypo- or hypergammaglobulinemia Autoantibodies (AIHA, ITP) Raynaud's phenomenon 	

Signs and Symptoms of Chronic GVHD (Continued)

Organ or Site	Diagnostic Feature(s) (Sufficient to Establish the Diagnosis of cGVHD)	Distinctive Features ^a (Seen in cGVHD, but Insufficient Alone to Establish a Diagnosis)	Other Features or Unclassified Entities (cGVHD Manifestations if Diagnosis is Confirmed)	Common (Seen With Both Acute and Chronic GVHD)
Other			Pericardial or pleural effusions	
			• Ascites	
			Peripheral neuropathy	
			Nephrotic syndrome	
			Myastenia gravis	
			Cardiac conduction abnormality or cardiomyopathy	

AIHA = autoimmune hemolytic anemia; ALT = alanine aminotransferase; ITP = idiopathic thrombocytopenic $\begin{array}{l} purpura; \ PFTs = pulmonary \ function \ tests. \\ ^{a} \ In \ all \ cases, \ infection, \ drug \ effect, \ malignancy, \ or \ other \ causes \ must \ be \ excluded. \end{array}$

^b BOS can be diagnostic for lung cGVHD only, if distinctive sign or symptom present in another organ

APPENDIX D. STAGING OF CHRONIC GVHD (NIH CRITERIA)

The definitions for mild, moderate, and severe chronic GVHD are as follows:

NIH Global Severity of Chronic GVHD

Mild Chronic GVHD

- 1 or 2 organs involved with no more than score 1 *plus*
- Lung score 0

Moderate Chronic GVHD

• 3 or more organs involved with no more than score 1

OR

• At least 1 organ or site with a max score of 2

OR

• Lung score 1

Severe Chronic GVHD

• At least 1 organ with a score of 3

OR

• Lung score of 2 or 3

Key points:

- In skin: higher of the 2 scores to be used for calculating global severity.
- In lung: FEV₁¹ is used instead of clinical score for calculating global severity.
- If the entire abnormality in an organ is noted to be unequivocally explained by a non-GVHD documented cause, that organ is not included for calculation of the global severity.
- If the abnormality in an organ is attributed to multifactorial causes (GVHD plus other causes), the scored organ will be used for calculation of the global severity regardless of the contributing causes (no downgrading of organ severity score).

Staging of chronic GVHD as described by Jagasia et al (2015) should be performed using scoring criteria as described below.

 $^{^{1}}$ The FEV₁ is the volume exhaled during the first second of a forced expiratory maneuver started from the level of total lung capacity.

Staging of Chronic GVHD (Jagasia et al 2015)

	SCORE 0	SCORE 1	SCORE 2	SCORE 3
PERFORMANCE SCORE: KPS ECOG LPS	☐ Asymptomatic and fully active (ECOG 0; KPS or LPS 100%)	☐ Symptomatic, fully ambulatory, restricted only in physically strenuous activity (ECOG 1, KPS or LPS 80-90%)	☐ Symptomatic, ambulatory, capab of self-care, >50% of waking hours o of bed (ECOG 2, KPS or LPS 60- 70%)	>50% of waking
SKIN† SCORE % BSA GVHD features to be score by BSA: Check all that apply: Maculopapular rash/eryt Lichen planus-like featu Sclerotic features Papulosquamous lesions ichthyosis Keratosis pilaris-like GV	involved thema tres	□ 1-18% BSA	□ 19-50% BSA	□ >50% BSA
SKIN FEATURES SCORE:	□ No sclerotic features		☐ Superficial sclerotic features "not hidebound" (able to pinch)	Check all that apply: ☐ Deep sclerotic features ☐ "Hidebound" (unable to pinch) ☐ Impaired mobility ☐ Ulceration
Other skin GVHD features Check all that apply: Hyperpigmentation Poikiloderma Severe or generalized point involvement Nail involvement Abnormality present but	ruritus	on-GVHD documented	cause (specify):	
MOUTH Lichen planus-like features present: Yes No Abnormality present but	☐ No symptoms explained entirely by no	☐ Mild symptoms with disease signs but not limiting oral intake significantly on-GVHD documented	☐ Moderate symptoms with disease signs with partial limitation of oral intake d cause (specify):	☐ Severe symptoms with disease signs on examination with major limitation of oral intake

Organ scoring of chronic GVHD. ECOG indicates Eastern Cooperative Oncology Group; KPS, Karnofsky performance status; LPS, Lansky performance status; BSA, body surface area; ADL, activities of daily living; LFTs, liver function tests; AP, alkaline phosphatase; ALT, alanine aminotransferase; ULN, normal upper limit. *Weight loss within 3 months. †Skin scoring should use both percentage of BSA involved by disease signs and the cutaneous features scales. When a discrepancy exists between the percentage of total body surface (BSA) score and the skin feature score, OR if superficial sclerotic features are present (Score 2), but there is impaired mobility or ulceration (Score 3), the higher level should be used for the final skin scoring. To be completed by specialist or trained medical providers. **Lung scoring should be performed using both the symptoms and FEV₁ scores whenever possible. FEV₁ should be used in the final lung scoring where there is discrepancy between symptoms and FEV₁ scores.

Staging of Chronic GVHD (Continued)

	SCORE 0	SCORE 1	SCORE 2	SCORE 3
EYES Keratoconjunctivitis sicca (KCS) confirmed by ophthalmologist: Yes No Not examined	□ No symptoms	 Mild dry eye symptoms not affecting ADL (requirement of lubricant eye drops ≤ 3 x per day) 	■ Moderate dry eye symptoms partially affecting ADL (requiring lubricant eye drops > 3 x per day or punctal plugs), WITHOUT new vision impairment due to KCS	Severe dry eye symptoms significantly affecting ADL (special eyeware to relieve pain) OR unable to work because of ocular symptoms OR loss of vision due to KCS
☐ Abnormality present b	ut explained entirely b	y non-GVHD documente	ed cause (specify):	
GI Tract Check all that apply: □ Esophageal web/ proximal stricture or ring □ Dysphagia □ Anorexia □ Nausea □ Vomiting □ Diarrhea □ Weight loss ≥5%* □ Failure to thrive □ Abnormality present b	□ No symptoms ut explained entirely h	□ Symptoms without significant weight loss* (<5%)	☐ Symptoms associated with mild to moderate weight loss* (5-15%) OR moderate diarrhea without significant interference with daily living	□ Symptoms associated with significant weight loss* >15%, requires nutritional supplement for most calorie needs OR esophageal dilation OR severe diarrhea with significant interference with daily living
LIVER	□ Normal total bilirubin and ALT or AP < 3 x ULN ut explained entirely b	□ Normal total bilirubin with ALT ≥3 to 5 x ULN or AP ≥ 3 x ULN by non-GVHD documente	☐ Elevated total bilirubin but ≤3 mg/dL or ALT > 5 ULN ed cause (specify):	☐ Elevated total bilirubin > 3 mg/dL
Lungs**				
Symptom score:	□ No symptoms	☐ Mild symptoms (shortness of breath after climbing one flight of steps)	☐ Moderate symptoms (shortness of breath after walking on flat ground)	☐ Severe symptoms (shortness of breath at rest; requiring 0 ₂)
Lung score: % FEV1	□ FEV1≥80%	□ FEV1 60-79%	□ FEV1 40-59%	□ FEV1 < 39%
Pulmonary function tests Not performed		arms :		
☐ Abnormality present bi	it explained entirely b	y non-GVHD documente	ed cause (specify):	

Organ scoring of chronic GVHD. ECOG indicates Eastern Cooperative Oncology Group; KPS, Karnofsky performance status; LPS, Lansky performance status; BSA, body surface area; ADL, activities of daily living; LFTs, liver function tests; AP, alkaline phosphatase; ALT, alanine aminotransferase; ULN, normal upper limit. *Weight loss within 3 months. †Skin scoring should use both percentage of BSA involved by disease signs and the cutaneous features scales. When a discrepancy exists between the percentage of total body surface (BSA) score and the skin feature score, OR if superficial sclerotic features are present (Score 2), but there is impaired mobility or ulceration (Score 3), the higher level should be used for the final skin scoring. To be completed by specialist or trained medical providers. **Lung scoring should be performed using both the symptoms and FEV_1 scores whenever possible. FEV_1 should be used in the final lung scoring where there is discrepancy between symptoms and FEV_1 scores.

Staging of Chronic GVHD (Continued)

	SCORE 0	SCORE 1	SCORE 2	SCORE 3
P-ROM score (see below) Shoulder (1-7): Elbow (1-7): Wrist/finger (1-7): Ankle (1-4):	□ No symptoms t explained enti	☐ Mild tightness of arms or legs, normal or mild decreased range of motion (ROM) AND not affecting ADL	☐ Tightness of arms or legs OR joint contractures, erythema thought due to fasciitis, moderate decrease ROM AND mild to moderate limitation of ADL	□ Contractures WITH significant decrease of ROM AND significant limitation of ADL (unable to tie shoes, button shirts, dress self etc.)
a storio many present on	r capitalinear cities		1.	
GENITAL TRACT (See Supplemental figure) Not examined Currently sexually active Yes No	□ No signs	☐ Mild signs [‡] and females with or without discomfort on exam	☐ Moderate signs [‡] and may have symptoms with discomfort on exam	☐ Severe signs [‡] with or without symptoms
☐ Abnormality present bu	t explained enti	rely by non-GVHD docun	nented cause (specify):	
			hronic GVHD (check all able none – 0,mild -1, mo	
☐ Ascites (serositis)	□ Mya	asthenia Gravis		
☐ Pericardial Effusion_	_ □ Peri	pheral Neuropathy	□ Eosino	philia > 500/μl
☐ Pleural Effusion(s)	□ Poly	ymyositis	□ Platele	ets <100,000/µl
☐ Nephrotic syndrome	□ Wei	ight loss>5%* without GI	symptoms Others	(specify):
Overall GVHD Severity (Opinion of the evaluator)) D No C	GVHD Mild	☐ Moderate	☐ Severe

Organ scoring of chronic GVHD. ECOG indicates Eastern Cooperative Oncology Group; KPS, Karnofsky performance status; LPS, Lansky performance status; BSA, body surface area; ADL, activities of daily living; LFTs, liver function tests; AP, alkaline phosphatase; ALT, alanine aminotransferase; ULN, normal upper limit. *Weight loss within 3 months. †Skin scoring should use both percentage of BSA involved by disease signs and the cutaneous features scales. When a discrepancy exists between the percentage of total body surface (BSA) score and the skin feature score, OR if superficial sclerotic features are present (Score 2), but there is impaired mobility or ulceration (Score 3), the higher level should be used for the final skin scoring. To be completed by specialist or trained medical providers. **Lung scoring should be performed using both the symptoms and FEV_1 scores whenever possible. FEV_1 should be used in the final lung scoring where there is discrepancy between symptoms and FEV_1 scores.

APPENDIX E. RESPONSE ASSESSMENT FOR CHRONIC GVHD (NIH CRITERIA)

Response will be assessed using NIH 2014 criteria (Lee et al 2015)

a) Response determination for cGVHD by organ at postbaseline assessment

(comparison versus baseline)

Organ	Complete Response	Partial Response	Progression
Skin	NIH Skin Score 0 after previous involvement	Decrease in NIH Skin Score by 1 or more points	Increase in NIH Skin Score by 1 or more points, except 0 to 1
Eyes	NIH Eye Score 0 after previous involvement	Decrease in NIH Eye Score by 1 or more points	Increase in NIH Eye Score by 1 or more points, except 0 to 1
Mouth	NIH Modified OMRS 0 after previous involvement	Decrease in NIH Modified OMRS of 2 or more points	Increase in NIH Modified OMRS of 2 or more points
Esophagus	NIH Esophagus Score 0 after previous involvement	Decrease in NIH Esophagus Score by 1 or more points	Increase in NIH Esophagus Score by 1 or more points, except 0 to 1
Upper GI	NIH Upper GI Score 0 after previous involvement	Decrease in NIH Upper GI Score by 1 or more points	Increase in NIH Upper GI Score by 1 or more points, except 0 to 1
Lower GI	NIH Lower GI Score 0 after previous involvement	Decrease in NIH Lower GI Score by 1 or more points	Increase in NIH Lower GI Score by 1 or more points, except from 0 to 1
Liver	Normal ALT, alkaline phosphatase, and Total bilirubin after previous elevation of 1 or more	Decrease by 50%	Increase by 2 × ULN
Lungs	Normal FEV1% after previous involvement If PFTs not available, NIH Lung Symptom Score 0 after previous involvement	Increase by 10% predicted absolute value of FEV1% If PFTs not available, decrease in NIH Lung Symptom Score by 1 or more points	 Decrease by 10% predicted absolute value of FEV1% If PFTs not available, increase in NIH Lung Symptom Score by 1 or more points, except 0 to 1
Joints and fascia	Both NIH Joint and Fascia Score 0 and P-ROM score 25 after previous involvement by at least 1 measure	Decrease in NIH Joint and Fascia Score by 1 or more points or increase in P-ROM score by 1 point for any site	Increase in NIH Joint and Fascia Score by 1 or more points or decrease in P-ROM score by 1 point for any site
Global	Clinician overall severity score 0	Clinician overall severity score decreases by 2 or more points on a 0-10 scale	Clinician overall severity score increases by 2 or more points on a 0-10 scale

Source: Adapted from Lee et al 2015.

b) Response assessment for chronic GVHD by organ at baseline and at each post-baseline visit

Health Care Provider Global Ratings: 0=none 1= mild 2=moderate 3=severs		uld you rate the severity of this patient's chronic GvHD symptoms on the following scale, • cGVHD symptoms that are not at all severe and 10 is the most severe cGVHD symptoms 1 2 3 4 5 6 7 8 9 10 • 12 1 4 5 6 7 8 9 10 • 12 1 4 10 wors • 10 4 1 4 10 wors • 10 4 10 4 10 10 10 10 10 10 10 10 10 10 10 10 10					h better ly better ter same se worse	ald you say that this	patient's cG	vHD is					
Mouth		Erythema	None	0		f eryther erate ery (<25%	thema	1	-	Moderate Severe	e (≥25%) or erythema 25%)	2	Severe erythe (≥25%)	ema	3
		Lichenoid	None	0	Liche	n-like ch	nanges	1	l	ichen-li	ke changes -50%)	2	Lichen-like cha (>50%)	inges	3
		Ulcers	None	0		1 2070			Uli		olving (≤20%)	3	Severe ulcera (>20%)	tions	6
									-		Total sco	re for a	II mucosal ch	anges	
Gastrointestinal-Esopi Dysphagia OR Odynophagia Gastrointestinal-Upper Early satiety OR Angrexia OR Nausea & Vomiti Gastrointestinal-Lowe	r GI	0= no esophageal s 1=Occasional dyspl 2=Intermittent dyspl 3=Dysphagia or ody 0= no symptoms 1=mild, occasional s 2=moderate, interm 3=more severe or p 0= no loose or liquid 1= occasional loose	nagia or nagia or nophag sympton ittent syi ersisten i stools e or liqui	odynopha odynopha ia for almo ns, with litt mptoms, w t symptom during the id stools, o	gia with ast all ora le reduct with some is through past week in some	solid for al intake, ion in or a reducti hout the ak days du	on alm on alm al intak on in o day, w	oills, but nost even se during ral intake with marke	oot for lic v day of the pas during ed reduce	quids or the pas t week the past ction in c	t week week ral inlake, on	almost ev	ery day of the past		
Line Arm		2=intermittent loose volume depletion 3=voluminous diam	بنشام									mar in		prevent or co	rrect
Lungs (Liters and % pr Bronchloitis Obli		FEV1	FVC					oth DLCO				TLC		RV	
Liver Values		Total serum bilirubin mg/o	ULN		g/dL	ALT		U/L	0	EN	U/L	Alkaline	Phosphatase U/L	ULN	U/L
Baseline Values		Total Distance Walker	2	1 2 min	□ 6 min			or Lansky	K/u			Total WE	K/ut	Eosinophils	%
		Abnormality present Abnormality present Abnormality present	but expl	ained entire	ly by nan-	-GVHD d	ocumen	ted cause	(specify	site/alten	nate cause):				

	SCORE 0	SCORE 1	SCORE 2	SCORE 3		
SKIN	No BSA	1-18% BSA	19-50% BSA	>50% BSA		
GVHD features to be scored by BSA: Check all that apply: Maculopapular rash / erythema Lichen planus-like features Sclerotic features Papulosquamous lesions or ichthyosis Keratosis pilaris-like Abnormality present but ex		CVIID I				
Abhormanty present but ex	plained entirely by	non-GVAD documented	r cause (specify)			
SKIN FEATURES SCORE: If skin features score = 3, BS.	No sclerotic features	le colorecie/fosciitie	Superficial sclerotic features "not hidebound" (able to pinch)	Check all that apply: Deep sclerotic features "Hidebound" (unable to pinch) Impaired mobility Ulceration		
	severity of this patie	ent's skin and/or joint ti	ghtening on the following so 9 10 Most severe symptoms possible	ale, where 0 is not at all		
				I		
EYES	No symptoms symptoms	Mild dry eye symptoms not affecting ADL (requirement of lubricant eye drops ≤ 3 x per day)	Moderate dry eye symptoms partially affecting ADL (requiring lubricant eye drops > 3 x per day or punctal plugs), WITHOUT new vision impairment due to KCS	Severe dry eye symptoms significantly affecting ADL (special eyeware to relieve pain) OR unable to work because of ocular symptoms OR loss of vision due to KCS		
Abnormality present but ex	plained entirely by	non-GVHD documented	d cause (specify):			
Lungs No symptoms		Mild symptoms (shortness of breath after climbing one flight of steps)	Moderate symptoms (shortness of breath after walking on flat ground)	Severe symptoms (shortness of breath at rest; requiring 0_2)		
Abnormality present but explained entirely by non-GVHD documented cause (specify):						

	SCORE 0	SCORE 1	SCORE 2	SCORE 3		
JOINTS AND FASCIA	No symptoms	Mild tightness of	Tightness of arms or	Contractures WITH		
		arms or legs, normal	legs OR joint contractures,	significant decrease of		
		or mild decreased	erythema thought due to	ROM AND significant		
		range of motion	fasciitis, moderate	limitation of ADL		
		(ROM) AND not	decrease ROM AND mild	(unable to tie shoes,		
		affecting ADL	to moderate limitation of	button shirts, dress self		
			ADL	etc.)		
Abnormality present but explained entirely by non-GVHD documented cause (specify):						

All abnormalities should be documented; however, the organ is not evaluable if there is another well-documented non-chronic GVHD cause.

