8.2.2. Chronic GVHD Response Assessment

Chronic GVHD organ scoring and the overall severity score 0 to 10 will be assessed on Day 1 (ie, baseline). Postbaseline response evaluations will be performed by the treating physician according to the detailed schedule in Table 4. At each postbaseline assessment, each organ must be assessed using the same criteria as for baseline, and response should be determined by comparing the current organ assessment with the baseline organ assessment on Day 1. A high level summary of organ-specific response assessment criteria as per NIH consensus guideline (Lee et al 2015, Appendix E) are listed in Table 18 and Table 19.

Table 18: Organ Assessments

Organ	Evaluation	Criteria
Skin	NIH Skin Score, considering %BSA involvement and sclerotic features	Change of Skin score
Eyes	NIH Eye score	Change of Eye score
Mouth	NIH Modified OMRS (sum of scores for erythema, lichenoid, and ulcers)	Change of OMRS
Esophagus	NIH Esophagus score	Change in Esophagus score
Upper GI	NIH Upper GI score	Change in Upper GI score
Lower GI	NIH Lower GI score	Change of Lower GI score
Liver	Lab results for ALT, ALP, and total bilirubin	Change in values of lab results
Lungs	NIH Lung score and FEV1% (in participants using a bronchodilator, the post-bronchodilator response should be used for response assessment)	Change in FEV1%
Joints and fascia	NIH Joint and Fascia score and P-ROM scores	Change of Joint and Fascia score and P-ROM scores

Table 19: Postbaseline Response Evaluations

Organ	Organ Specific Response				
Skin	CR/not involved	PR in at least	PR or CR in 1 or	Progression in	Organ-specific
Eyes		1 organ with baseline	more organ(s) with baseline	1 or more	response 'unchanged' for
Mouth		involvement	involvement	organ(s) with baseline	all organs (incl.
Esophagus		AND .	AND	involvement	no involvement)
Upper GI		no progression in any other	progression in 1 or more	OR new occurrence	
Lower GI		organ (ie, CR,	organs (incl.	in an organ with	
Liver		PR, unchanged,	new occurrence	no baseline	
Lungs		or no involvement)	in an organ with no baseline	involvement AND	
Joints and fascia			involvement)	no CR or PR in any other organ	
Overall Response	CR	PR	MR	PD	Unchanged

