10.4.1. Primary Analysis

10.4.1.1. Part 1 and Safety Run-In for Part 1 Expansion

The toxicity of itacitinib will be monitored continuously for each treatment group using the Bayesian approach of Thall et al (1995, 1996) as extended by Thall and Sung (1998). Dose-limiting toxicities are defined in Section 6.1.1.3.

Historical data on similar patients show a toxicity rate of 25%. The probability of toxicity for the historical data is modeled by beta distribution (Beta [25, 75]). The prior probability of toxicity for the experimental regimen is also modeled by beta distributions (Beta [0.5, 1.5]), which have the same means as the corresponding beta distributions for the historical data. Denoting the historical probability of toxicity rate by p(TOX,H), the following decision criteria will be applied:

Stop if Prob
$$\{p(TOX,H) + \delta TOX < p(TOX,E) | data \} > 0.95$$
, where $\delta TOX = 0$

Participants from each treatment group will be monitored according to the following nonbinding stopping boundaries for toxicity in Table 25. If a boundary is reached, the sponsor and external DMC will investigate and decide on the most appropriate action.

Table 25: Toxicity Stopping Boundaries

# Participants (Inclusive)	Number of DLTs Required to Stop (Inclusive)
1-2	No limit
3-4	3
5-6	4
7-9	5
10-11	6
12-14	7
15-17	8
18-19	9
20	9

10.4.1.2. Part 2

The primary endpoint is Month 6 response rate, defined as the proportion of participants demonstrating a CR or PR at Month 6 as per standard criteria (Lee et al 2015). The comparison of Month 6 response rate between treatment cohorts will be conducted once the last participant completes the Month 6 visit or withdraws from the study. A CMH test with normal approximation will be used. Summary statistics and 95% CI will be provided.

Participants who have missing data for the Month 6 response rate assessment will be considered as nonresponders.

For the interim analysis, the statistical assumptions are specified in Section 10.5.

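### Table 19 treats any newly involved organ as progression, while Appendix E exempts a 0-to-1 rise in most scored organs, so one Month 6 assessment can be a partial response under one text and a mixed response under the other

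*Protocol*

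**What the plan says.** Response in Part 2 is defined in Protocol 10.4.1.2: "Month 6 response rate, defined as the proportion of participants demonstrating a CR or PR at Month 6 as per standard criteria". Mixed response, progression and unchanged disease therefore all count as nonresponse.

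Two places bear on whether an organ has progressed.

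- **Appendix E, part (a)**, works organ by organ. Skin, eyes, esophagus, upper GI and lower GI each exempt a rise from 0 to 1; the eye entry reads "Increase in NIH Eye Score by 1 or more points, except 0 to 1". For lungs the exemption applies to the symptom score, and only when pulmonary function tests are not available. Mouth needs a rise of at least 2 points on its own scale, liver uses laboratory multiples, and joints and fascia have no exemption.
- **Table 19 in Protocol 8.2.2** combines organs into overall response. Its PD column accepts worsening of an organ involved at baseline, "OR new occurrence" in a previously clear organ. Its MR column includes new involvement "in an organ with no baseline" involvement as a form of progression. Neither cell sets a threshold. The PD column also requires "no CR or PR in any other organ", and the PR column requires "no progression in any other" organ.

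Protocol 8.2.2 introduces Tables 18 and 19 as "A high level summary of organ-specific response assessment criteria as per NIH consensus guideline" and points to Appendix E. Neither document defines a new occurrence or says which text prevails.

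**The concern.** Protocol Appendix D treats an organ at score 1 as involved, since three such organs make moderate disease. A physician using Table 19 will therefore naturally read a move from 0 to 1 as a new occurrence, and so as progression. A physician, or a programmer, working from Appendix E will not.

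Response is scored by the treating physician (Protocol 8.2.2). It is the Part 2 primary endpoint and, at Months 3 and 6, the key secondary endpoint of the expansion, which supports the Part 2 dose decision (Protocol 6.1.1.4). Without one rule, classification can depend on which page was used. Parts 1 and 1 expansion are open-label, so there the choice of reading could also be made with the arm known.

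A second route exists. SAP 7.3.1, which covers Part 1 and the expansion, makes a participant a nonresponder if cGVHD progression per NIH response criteria occurred at or before the timepoint. It does not say whether a new score of 1 is progression, so an early visit read as PD could cancel a later response.

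**Working it through.** **1. Side by side, for an organ scored 0 at baseline and 1 now**

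| Organ | Appendix E | Table 19 wording |
|---|---|---|
| Skin, eyes, esophagus, upper GI, lower GI | Not progression | New occurrence, so progression |
| Lungs, no pulmonary function tests (symptom score) | Not progression | New occurrence, so progression |
| Lungs, tests available | Decided by FEV1%, no such exemption | New occurrence, no threshold |
| Joints and fascia | Progression | New occurrence, so progression |
| Mouth, liver | Other thresholds | New occurrence, no threshold |

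The explicit exemption covers 5 of the 9 organs outright, and 6 of 9 counting the lung condition.

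**2. Which overall categories can differ**

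Take two organs involved at baseline (each CR, PR, unchanged or progressed) and two not involved (each still clear, 0 to 1, or 0 to 2 or more). That gives 4 × 4 × 3 × 3 = 144 combinations. Classify each with the Table 19 grid twice, once counting 0 to 1 as progression and once exempting it. Overall CR is taken to require that every organ be in CR or uninvolved.

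The results differ only if at least one clear organ moved 0 to 1 and nothing else progressed:

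- Clear organs: 2 × 2 − 1 = 3 patterns.
- Involved organs without progression: 3 × 3 = 9 patterns, of which 8 contain a CR or PR and 1 is unchanged in both.
- PR under Appendix E, MR under Table 19: 8 × 3 = 24.
- Unchanged under Appendix E, PD under Table 19: 1 × 3 = 3.
- PR under one and PD under the other: 0.

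So 27 of 144 combinations are discordant, and 24 of them change responder status at that visit. These count patterns, not patients, and say nothing about frequency.

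**3. Illustrative effect on Part 2 power**

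Inputs from the Protocol: 123 per arm (Table 3) and one-sided 0.025 (10.3). Assumed: response rates of 70% and 50%, and a fraction r of responders in both arms who become mixed responses when 0 to 1 counts.

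Power = Φ[(d − 1.96 × SE0) / SE1], where d is the rate difference, SE0 = √(2·p̄(1−p̄)/123) and SE1 = √((p1(1−p1) + p2(1−p2))/123).

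| r | Rates | d | SE0 | SE1 | Power |
|---|---|---|---|---|---|
| 0 | 70.0% v 50.0% | 0.200 | 0.0625 | 0.0612 | 90% |
| 5% | 66.5% v 47.5% | 0.190 | 0.0631 | 0.0620 | 86% |
| 10% | 63.0% v 45.0% | 0.180 | 0.0636 | 0.0625 | 81% |
| 15% | 59.5% v 42.5% | 0.170 | 0.0637 | 0.0628 | 76% |

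With 74.3% v 57.1% instead (26/35 v 20/35, a pair of counts from Table 23), the same steps give 81%, 75%, 69% and 64%.

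**4. Illustrative effect on the expansion**

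This uses the printed cells of Protocol Table 23 (SAP Table 3). With 28 itacitinib and 20 control responders out of 35 each, the posterior is 73.9%. Moving about 10% of responders in both arms to mixed response (3/28 = 10.7%, 2/20 = 10.0%) gives 25 v 18, printed as 64.3%. The fall is 9.6 percentage points.

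**The case against.** The best defence is that the documents already point to Appendix E. Section 8.2.2 calls the tables a summary, Appendix E says response is assessed by the NIH 2014 criteria, and both Protocol 10.4.1.2 and SAP 7.3.1 appeal to standard or NIH criteria. An exemption for 0 to 1 can only operate in an organ scored 0 at baseline, so if every new occurrence were progression the exemptions would do nothing. Table 19's PR column asks only for no progression elsewhere, and skin PR with a new eye score of 1 can be read as meeting that.

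This is a plausible reading and probably the intended one. It is not stated, however. Appendix E has no overall grid, so Table 19 has to be used to combine organs, and its MR cell expressly includes new occurrence. Followed literally, it gives a different Month 6 result from the organ criteria it is meant to summarize.

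Some stronger inferences fail:

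- **A PR becoming PD.** Table 19's PD column rules this out, because no other organ may be in CR or PR.
- **An unconditional lung exemption.** It applies only without pulmonary function tests, and FEV1% is scheduled at Day 180.
- **A fall in Table 23 from 73.9% to 45.0%.** That compares 28 v 20 with 25 v 20 and so reclassifies the itacitinib arm alone, for which the documents give no basis.
- **Demonstrated bias in Part 2.** Part 2 is double-blind, and the calculation shows possible loss of power only. It applies the stricter rule to everyone, so it does not measure inconsistency between sites.

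**Conclusion.** The two texts conflict, and the conflict reaches the primary endpoint. A new score of 1 in an exempt organ, alongside a response elsewhere and no other progression, is PR by Appendix E and mixed response by Table 19. With no response elsewhere it is unchanged by one and PD by the other. That second pair is nonresponse at the visit either way, but in the expansion an earlier PD could trigger the prior-progression rule in SAP 7.3.1.

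The size is not known. The loss of roughly 4 to 14 power points (90% to 86%, 81% or 76%) rests on assumed rates of 70% v 50%, an assumed 5% to 15% of responders affected, the same fraction in both arms, and a design that had the lenient rule in mind. The Table 23 shift from 73.9% to 64.3% likewise assumes about 10% in both arms, and the expansion has no formal test. The SAP supplied covers only Part 1 and the expansion, so it contains no Part 2 derivation that could settle the matter. The case for correction rests on the contradictory definition, not on these figures.

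**What to change.** For the response endpoint, reword the MR and PD cells of Table 19 so that a newly affected organ counts only if it meets Appendix E's definition of progression. State in Protocol 8.2.2 and SAP 7.3.1, and in the Part 2 analysis plan when written, that this rule governs both response at the timepoint and prior progression. Derive overall response in the analysis from the recorded organ scores with that rule, and list every assessment where the derived category differs from the site's call.

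GVHD progression also drives withdrawal from study treatment under Protocol 7.1.1. The passages must be reconciled there too; which clinical rule should apply is for the sponsor to decide.

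The cost is two table cells, a sentence in each plan and one derivation. Section 8.2.2 already requires every organ to be assessed at each postbaseline assessment. The case report form is not among the documents, so the sponsor should confirm that it captures the individual scores.
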